5.7. Criteria for Study Discontinuation

A subject will be discontinued from the study for any 1 of the following reasons:

- The subject has died.
- The subject is considered lost-to-follow-up when he/she repeatedly fails to return for scheduled visits and is unable to be contacted by the study site (eg, after 3 telephone calls and/or a certified letter or local equivalent).
- Informed consent is withdrawn.
- The study is terminated by the sponsor.
- The study is terminated by the local health authority, IRB or IEC.

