The occurrence of AEs should be sought by nondirective questioning of the subject during the screening process after signing the ICF and at each visit during the study. Adverse events may also be detected when they are volunteered by the subject during the screening process or between visits, or through physical examination, laboratory test, or other assessments. To the extent possible, each AE should be evaluated to determine:

- The severity grade (CTCAE Grade 1 to 5).
- Whether there is at least a reasonable possibility that the AE is related to the study treatment: suspected (yes) or not suspected (no).
- The start and end dates, unless unresolved at final follow-up.
- The action taken with regard to study drug.
- The event outcome (eg, not recovered/not resolved, recovered/resolved, recovering/resolving, recovered/resolved with sequelae, fatal, unknown).
- The seriousness, as per serious adverse event (SAE) definition provided in Section 8.3.1.

Unlike routine safety assessments, SAEs are monitored continuously and have special reporting requirements (see Section 8.3.2).

All AEs should be treated appropriately. If an AE is treated with a concomitant medication or nondrug therapy, this action should be recorded on Adverse Event form and the treatment should be specified on the Prior/Concomitant Medications or Procedures and Non-Drug Therapy form in the eCRF.

Once an AE is detected, it should be followed until it has resolved or until it is judged to be permanent; assessment should be made at each visit (or more frequently if necessary) of any changes in severity, the suspected relationship to the study drug, the interventions required to treat the event, and the outcome.

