8.3. Serious Adverse Events

8.3.1. Definitions

An SAE is defined as an event that meets at least 1 of the following criteria:

- Is fatal or life-threatening.
- Requires inpatient hospitalization or prolongation of existing hospitalization, unless hospitalization is a result of:
 - A routine treatment or monitoring of the studied indication not associated with any deterioration in condition.
 - An elective surgery or preplanned treatment for a pre-existing condition that is unrelated to the indication under study and has not worsened since signing the ICF.
 - A treatment on an emergency outpatient basis for an event not fulfilling any of the definitions of a SAE and not resulting in hospital admission.
 - Any social reasons and respite care, in the absence of any deterioration in the subject's general condition.
- Results in persistent or significant disability, incapacity, or a substantial disruption of a person's ability to conduct normal life functions.
- Constitutes a congenital anomaly or birth defect.
- Is considered to be an important medical event or a medically significant event that may not result in death, be immediately life-threatening, or require hospitalization but may be considered serious when, based on appropriate medical judgment, the event may jeopardize the subject or may require medical or surgical intervention to prevent 1 of the outcomes listed above.

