The longest duration of a TEAE of any grade is defined as the longest interval between the date of occurrence of a TEAE and the date of resolution. The longest duration of a Grade 3 or higher TEAE is defined as the longest interval between the date of occurrence of a Grade 3 or higher TEAE and the date of improvement to Grade 2 or lower. If participants have missing or partial onset/end date of a TEAE, the partial or missing dates will be handled using the rules explained in Section 4.1.4. Participants who have missing end date of a TEAE at the time of analysis will be right-censored using the following algorithm:

- If the TEAE is serious, then the participant will be censored at the earlier date of data cutoff, study discontinuation, and death.
- If the TEAE is not serious,
  - If the participant is ongoing with study treatment, then the participant will be censored at the data cutoff date, OR
  - If the participant discontinued treatment, then the participant will be censored at date of safety follow-up visit, or 35 days after the end of treatment visit (or after the last dose if the end of treatment visit was not performed), whichever is later; the censored date will be truncated by the earlier date of data cutoff, study discontinuation, and death if beyond.

Longest duration of new or worsening Grade 3 or higher colitis, diarrhea, rash, and febrile neutropenia will be summarized. In addition, longest duration of new or worsening AEs of any grade will be summarized for colitis, diarrhea, and rash.

The total number of participants whose TEAE of any grade resolved or whose Grade 3 or higher TEAE improved to Grade 2 or lower and the number of participants censored will be summarized. The Kaplan-Meier estimate of median time to resolution/improvement and its 95% CIs will be provided, with the CIs calculated using the generalization of Brookmeyer and Crowley's method (1982) with log-log transformation (Klein and Moeschberger 1997). Resolution/improvement rates at selected timepoints will also be provided with 95% CIs calculated using Greenwood's formula to estimate the standard error.

TEAEs of special interest to be summarized may be adjusted based on emerging data.

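### SAP 9.2.2 censors at death in the time-to-resolution analysis of adverse events of special interest, so the Kaplan-Meier resolution rate is overstated whenever such a death precedes later resolutions

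*SAP*

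**What the plan says.** SAP 9.2.2 defines the longest duration of an event as running from onset to resolution (any grade), or from onset to improvement to Grade 2 or lower (Grade 3 or higher). The Grade 3 or higher analysis covers colitis, diarrhea, rash and febrile neutropenia. The any-grade analysis covers the first three.

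The censoring rule is introduced by "Participants who have missing end date of a TEAE at the time of analysis will be right-censored using the following algorithm". It has these branches:

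- **Serious event:** "If the TEAE is serious, then the participant will be censored at the earlier date of data cutoff, study discontinuation, and death".
- **Non-serious event, still on treatment:** censored at data cutoff.
- **Non-serious event, treatment discontinued:** censored at the later of the safety follow-up visit and a 35-day limit, but "the censored date will be truncated by the earlier date of data cutoff, study discontinuation, and death if beyond".

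The outputs are the numbers resolved or improved and censored, and then: "The Kaplan-Meier estimate of median time to resolution/improvement and its 95% CIs will be provided". In addition, "Resolution/improvement rates at selected timepoints will also be provided with 95% CIs", using Greenwood standard errors. SAP Appendix A places these in Table 3.2.29 and Figure 4.5.2.

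Two Protocol provisions bear on which branch applies. Section 8.3.1 makes an event serious if it "Is fatal or life-threatening", so a fatal event always falls in the serious branch. Section 5.7 lists "The subject has died" as a reason for study discontinuation, so that term in the rule gives no other route for a participant who dies.

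**The concern.** Kaplan-Meier uses the participants still at risk to stand in for those censored. That is reasonable at a data cutoff, when the event is still running and may yet resolve. It is not reasonable at death, because death before resolution rules resolution out. Removing these participants from the risk set spreads their weight over people who can still resolve, and the estimate moves toward resolution.

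The numbers at stake are the timepoint rates and the median, which a reader will take as the chance of recovering from a class toxicity and the time it takes. SAP 11.2 says these duration summaries were added in Amendment 1 to describe how long class-effect events last. Case counts per event may be small, in which case one or two deaths can move the curve visibly. No competing-risk estimate is planned, and deaths are pooled with administrative censoring in a single count.

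**Working it through.** The documents give no resolution rate or fatality rate for these events, so there is no planned figure to reproduce. The check applies the SAP rule to assumed data and compares two estimators.

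**Formulas.** Let n_j be the number at risk and d_j the number resolving at time t_j.

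- SAP rule (death censored): rate = 1 − S(t), with S(t) = Π(1 − d_j/n_j).
- Death as a competing event (Aalen-Johansen): F(t) = Σ S_all(t_j−) × d_j/n_j, where S_all drops at both resolutions and deaths. With no other censoring, F(t) is the number resolved by t divided by all cases.

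**Example 1 (assumed): 10 cases, one death on day 5, nine improvements on days 6 to 14.** After day 5 nine are at risk and all nine improve, so S(14) = 0 and the SAP rate is 100%. The competing-event rate is 9/10 = 90%.

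**Example 2 (assumed): 12 cases, deaths on days 5 and 8, resolutions on days 3, 4, 6, 7, 9, 10, 11, 12, 13 and 14.**

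- Days 3 and 4: (11/12)(10/11) = 10/12. The day 5 death leaves 9 at risk.
- Days 6 and 7: (8/9)(7/8) = 7/9. The day 8 death leaves 6 at risk.
- Days 9 and 10: (5/6)(4/5) = 4/6.
- S(10) = (10/12)(7/9)(4/6) = 0.432, so the SAP rate at day 10 is 57%. The competing-event rate is 6/12 = 50%.
- At day 14 the SAP rate is 100%. The competing-event rate is 10/12 = 83%.

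**Effect of the number and timing of deaths (assumed): 10 cases, no other censoring.** Resolutions fall between days 5 and 60. Early deaths precede every resolution; late deaths follow the last one.

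| Deaths | Timing | SAP final rate | Competing-event final rate | SAP median (day) | Competing-event median (day) |
|---|---|---|---|---|---|
| 0 | – | 100% | 100% | 20 | 20 |
| 1 | early | 100% | 90% | 25 | 25 |
| 2 | early | 100% | 80% | 25 | 30 |
| 3 | early | 100% | 70% | 30 | 40 |
| 1 | late | 90% | 90% | 20 | 20 |
| 2 | late | 80% | 80% | 20 | 20 |

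The bias needs a death that precedes later resolutions. The SAP curve reaches 100% exactly when the longest observed duration ends in resolution, however many died earlier. Some administrative censoring does not remove the problem: nine cases with two deaths and one administrative censoring gave 100% against 77.8%.

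**End dates.** The algorithm applies only when the end date is missing. Protocol 8.1.2 asks sites to record "The start and end dates, unless unresolved at final follow-up" and does not say what to enter for a fatal event. SAP 4.1.4 caps an imputed partial end date at the date of study discontinuation or death, so some events can acquire an end date equal to the date of death. SAP 9.2.2 does not say how these are to be treated.

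**The case against.** The strongest reply is that this is a descriptive safety summary with no hypothesis, group comparison or decision rule attached, and that deaths remain visible. The counts resolved and censored are shown with the Kaplan-Meier estimate. Events of special interest are tabulated by maximum severity, and fatal events have their own tables (SAP 9.2.3) and listing. Only four of the twelve listed events enter the duration analysis; pneumonitis, PJP infection, intestinal perforation and exfoliative dermatitis do not. No document suggests how many deaths to expect.

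All of this stands as a limit on importance. None of it corrects the rate or the median. The fatal-event tables also miss a participant who dies of something else, such as lymphoma, with serious colitis unresolved. That participant is censored at death here but is not a fatal colitis case.

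A reader might infer more than the text supports, in three ways:

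- **That a fatal event with the death date as its end date will be counted as resolved.** SAP 9.2.2 ends the interval at resolution or at improvement to Grade 2 or lower, and a Grade 5 event is neither. Protocol 8.1.2 also collects a fatal outcome separately from recovery. Such a case could be misread if programming used the end date alone, but the SAP does not direct it.
- **That a short fatal episode is displaced by a longer earlier one that resolved.** The censoring sentence is written for the participant, and the SAP does not say how resolved and unresolved episodes in one person compete. Displacement is one reading of unclear text.
- **That these figures are the trial's evidence that class toxicities are reversible.** The documents do not give them that role; the stated purpose is to describe duration.

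**Conclusion.** The point holds as a flaw in a descriptive analysis. SAP 9.2.2 makes death a censoring time for serious events, and for non-serious events after treatment discontinuation, in an analysis of a probability that death rules out. The resulting rate is too high whenever a death with the event unresolved precedes later resolutions, and the median can be too short. In the two worked examples the excess is 7 to 17 percentage points with one or two deaths among 10 to 12 cases.

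Those case counts and deaths are assumptions. With no such deaths, or with deaths only after the last resolution, the planned estimate is unbiased in this respect. It would therefore be wrong to read the rule as always giving 100%, or as concerning only events that were themselves fatal, since it applies to death from any cause. The size in this trial cannot be computed from the documents. The primary ORR analysis is unaffected. The change is worth making because it is cheap and the other safety tables do not substitute for it.

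**What to change.** In SAP 9.2.2, for the resolution/improvement analysis:

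1. Treat death from any cause before resolution or improvement as a competing event, and estimate the cumulative incidence of resolution or improvement by Aalen-Johansen. Keep censoring for data cutoff and for discontinuation other than death.
2. Take the timepoint rates and the median from that curve, with matching confidence intervals, in Table 3.2.29 and Figure 4.5.2. Report the median as not reached if the curve stays below 50%.
3. Report participants who died with the event unresolved separately from other censored participants.
4. State that an event with a fatal outcome, or whose end date is only the date of death (including dates imputed under SAP 4.1.4), is not a resolution or improvement.

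The definition of longest duration should stay as it is. A new rule for choosing among episodes would change what is measured and is not needed here.

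The cost is a short SAP amendment and reprogramming of one table and one figure, including replacement of the Kaplan-Meier confidence interval methods. The reported resolution rate may come out slightly lower. No new data are needed for item 4, since outcome is already collected. Items 3 and 4 alone would make the deaths visible but would leave the rate and median overstated.

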#### 9.2.3. Adverse Event Summaries

Overall summaries of TEAEs by treatment regimen will be provided during the INCB050465 initial QD dosing period, maintenance dosing period, and overall period (ie. all TEAEs regardless of the timing of occurrence). These summaries will include the following:

- Number (%) of participants reporting any TEAEs
- Number (%) of participants reporting any Grade 3 or higher TEAEs
- Number (%) of participants reporting any serious TEAEs
- Number (%) of participants reporting any TEAEs related to INCB050465
- Number (%) of participants reporting any Grade 3 or higher TEAEs related to INCB050465
- Number (%) of participants reporting any serious TEAEs related to INCB050465

- Number (%) of participants who had TEAE with fatal outcome
- Number (%) of participants with INCB050465 dose reductions because of TEAEs
- Number (%) of participants who temporarily interrupted INCB050465 because of TEAEs
- Number (%) of participants who permanently discontinued INCB050465 because of TEAEs

The following summaries will be produced for TEAEs during the overall period by MedDRA term (if 10 or fewer participants appear in a table, a listing may be appropriate):

- Summary of TEAEs by SOC and PT
- Summary of TEAEs by PT in decreasing order of frequency
- Summary of TEAEs by SOC, PT, and maximum severity
- Summary of TEAEs by PT and maximum severity in decreasing order of frequency
- Summary of Grade 3 or higher TEAEs by SOC and PT
- Summary of Grade 3 or higher TEAEs by PT in decreasing order of frequency
- Summary of serious TEAEs by SOC and PT
- Summary of serious TEAEs by PT in decreasing order of frequency
- Summary of INCB050465 treatment-related TEAEs by SOC and PT
- Summary of INCB050465 treatment-related TEAEs by PT in decreasing order of frequency
- Summary of INCB050465 treatment-related TEAEs by SOC, PT, and maximum severity
- Summary of Grade 3 or higher INCB050465 treatment-related TEAEs by SOC and PT
- Summary of INCB050465 treatment-related serious TEAEs by SOC and PT
- Summary of TEAEs with a fatal outcome by SOC and PT
- Summary of TEAEs leading to INCB050465 dose reduction by SOC and PT
- Summary of TEAEs leading to INCB050465 dose interruption by SOC and PT
- Summary of TEAEs leading to discontinuation of INCB050465 by SOC and PT
- Summary of selected TEAEs of special interest by maximum severity
- Summary of time to onset of selected TEAEs of special interest
- Summary of time to onset of selected TEAEs of special interest: life-table method
- Summary of longest duration of selected TEAEs of special interest

The following supporting summaries will be produced for TEAEs during the INCB050465 initial QD dosing period and the maintenance dosing period by MedDRA term. For the supporting summaries during the maintenance dosing period, participants who cross over to the selected treatment regimen after the start of the maintenance dosing period will be summarized in a separate group (ie, Crossover).

- Summary of TEAEs by PT in decreasing order of frequency
- Summary of TEAEs by PT and maximum severity in decreasing order of frequency
- Summary of Grade 3 or higher TEAEs by PT in decreasing order of frequency
- Summary of serious TEAEs by PT in descending order of frequency
- Summary of TEAEs with a fatal outcome by SOC and PT
- Summary of TEAEs leading to discontinuation of INCB050465 by SOC and PT

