During screening, subjects will have an objective assessment of disease status performed by CT scan or MRI. Subjects will also have a bone marrow biopsy performed at screening unless the subject has undergone a recent bone marrow biopsy. Disease status will be assessed (using the same modality from screening) every 8 weeks through Week 24, then every 12 weeks through Week 96, and then every 24 weeks thereafter until PD. On-study bone marrow biopsies will be required only if needed to confirm a CR.

Subjects withdrawn from study treatment for reasons other than disease progression will be followed for disease assessment until either radiologic disease progression, the start of a new anticancer therapy, consent withdrawal, or death (whichever occurs first). After permanently discontinuing study treatment, subjects will be followed every 12 weeks for subsequent anticancer therapies and survival.

Estimated Duration of Participation: Subject participation from screening through follow-up is expected to average approximately 25 months, which includes the following:

- A screening period lasting up to 28 days.
- A treatment period lasting as long as the subject is receiving benefit, tolerating the regimen, and has not met withdrawal criteria (approximately 52 weeks).
- A safety follow-up period lasting 30 to 35 days.
- A disease and survival follow-up period until the end of the study.

At the end of the study, subjects who have completed at least 24 months of study participation (starting from first dose of INCB050465), who remain on active study treatment, and who have no evidence of progressive disease will have the option to continue on monotherapy with INCB050465 provided within a rollover Protocol, as local law permits.

Estimated Number of Subjects: Approximately 120 subjects will be enrolled. The first 50 subjects will be assigned at 1:1 to Group A (INCB050465 20 mg once daily for 8 weeks followed by 20 mg once weekly) and Group B (INCB050465 20 mg once daily for 8 weeks followed by INCB050465 2.5 mg once daily). The remaining 70 subjects will be assigned to the selected treatment group (ie, either treatment Group A or treatment Group B).

Principal Coordinating Investigator:

- United States: [REDACTED], MD, [REDACTED], USA
- EU: [REDACTED], MD, PhD, [REDACTED], Czech Republic

Statistical Methods:

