Subjects will receive INCB050465 administered orally at a dose of 20 mg QD for 8 weeks. Based on an *ex vivo* whole blood assay, the 20 mg QD dose provides exposure ranging from approximately 2-fold above the IC₉₀ at trough to 19-fold above the IC₉₀ at peak. Data as of 02 SEP 2016 show that of the 11 NHL subjects who were administered 20 mg QD, 10 achieved an objective response at the time of first disease assessment (9 weeks). However, among all evaluable subjects with an objective response (n = 20), 7 subjects (35%) discontinued study treatment due to an AE. Consequently, after receiving 20 mg QD of INCB050465 for 8 weeks, subjects will receive either 20 mg once weekly or 2.5 mg QD of INCB050465.

The once-weekly regimen is proposed to maintain response while providing time off from pathway inhibition, which may reduce the frequency of AEs leading to study treatment withdrawal. Pharmacodynamic data from Study INCB 50465-101 showed that a single dose of 20 mg exhibited maximal inhibition of AKT in an *ex vivo* pharmacodynamic assay, and PK modeling suggests that 20 mg once weekly will 1) achieve maximal inhibition equivalent to approximately 10 × IC₉₀, 2) exceed the IC₉₀ for approximately 36 hours, and 3) have minimal to no inhibition for approximately half the dosing interval. This once-weekly regimen is similar to that of another PI3K inhibitor (copanlisib), which is administered intravenously on Days 1, 8, and 15 of a 28-day cycle ([Aliqopa 2017](#)).

The continuous QD regimen of INCB050465 has demonstrated prolonged responses in both aggressive and indolent NHL. One subject with FL who received a 10 mg QD dose achieved a complete metabolic response and remained on study treatment for approximately 13 months before withdrawing due to an AE (Grade 2 psoriasis). The 2.5 mg QD regimen is proposed to provide approximately 86% inhibition of the PI3K pathway on average but could reduce the frequency of AEs that lead to study treatment withdrawal.

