Timepoint	Dose (Group A)	Dose (Group B)
Starting dose	20 mg QD for 8 weeks (Day 1 through Day 56)	20 mg QD for 8 weeks (Day 1 through Day 56)
First dose reduction	10 mg QD	10 mg QD
Second dose reduction	5 mg QD	5 mg QD
Week 9 (Day 57) onward	20 mg once weekly ^a	2.5 mg QD ^b
First dose reduction	10 mg once weekly	1 mg QD ^c
Second dose reduction	5 mg once weekly	NA

^a All subjects will receive 20 mg once weekly at Week 9 (Day 57) regardless of prior dose level, unless a dose modification of a switch to a QW schedule before Week 9 is required for diarrhea/colitis management (see [Table 5](#)).

^b All subjects will receive 2.5 mg QD at Week 9 (Day 57) regardless of prior dose level, unless a dose modification of a switch to a QW schedule is required for diarrhea/colitis management (see [Table 5](#)).

^c Further dose modification due to diarrhea or colitis for subjects on 1 mg QD is permitted (see [Table 5](#)).

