#### 3. STUDY DESIGN

This is a Phase 2, multicenter, open-label study evaluating 2 INCB050465 treatment regimens based on the primary endpoint of ORR. Participants with relapsed or refractory FL (Grades 1, 2, or 3a) who have received at least 2 prior systemic therapies and who are ineligible for hematopoietic stem cell transplant will be screened for eligibility. A total of approximately 120 participants will be enrolled. The first 50 participants enrolled will be assigned at a 1:1 ratio to 2 study treatment regimens as follows (see Figure 1):

- Group A: INCB050465 20 mg QD for 8 weeks followed by 20 mg once weekly
- Group B: INCB050465 20 mg QD for 8 weeks followed by 2.5 mg QD

[figure not shown]
The remaining 70 participants will be allocated to 1 of the 2 treatment groups to better understand the safety and efficacy of that treatment regimen. The treatment group will be selected after evaluation of emerging safety and efficacy data from this and other monotherapy studies of INCB050465 in NHL, which are evaluating the same or similar dosing regimens, and will be implemented after the first 50 participants are enrolled. Participants allocated to the nonselected treatment regimen may switch to the selected treatment regimen or remain on their current treatment regimen, provided they have not met study-treatment withdrawal criteria, and there are no safety concerns for their current treatment regimen. There will be no rebaselining for participants who switch treatment regimens, and all participants will continue to follow the same assessment schedule.

Participants may receive treatment until disease progression, death, unacceptable toxicity, or consent withdrawal, whichever occurs first. Participants will be evaluated for ORR by an IRC and followed for CRR, DOR, PFS, OS, and safety.

An interim futility analysis is planned when the first 50 participants (Group A and Group B combined) have been evaluated for response or have permanently discontinued study treatment because of disease progression, withdrawal of consent, or death. The study will be terminated

for futility if  $\leq$  18 of the 50 participants have responded (ie, CR or PR) based on assessments provided by the IRC.

Figure 1: Study Design

<sup>a The first 50 subjects will be assigned at a 1:1 ratio to treatment Group A and treatment Group B. The remaining 70 subjects will be enrolled to the selected treatment Group (ie, either Group A or Group B).

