# **5.2.** Treatment Groups

This is a Phase 2, multicenter, open-label study. For the purpose of analysis, the 20 mg once weekly dosing period in Group A and the 2.5 mg QD dosing period in Group B are considered maintenance dosing periods. Data will be presented in summary tables by actual received treatment regimen and combined, with an exception for participants who cross over to the selected treatment regimen after the start of the maintenance dosing period. There will not be any statistical comparison between the treatment groups.

For participants who cross over from the initially assigned treatment regimen to the selected treatment regimen, if the crossover happens on/before the start of the maintenance period, then the participant will be summarized, according to the actual received treatment, in the selected treatment regimen; otherwise, the participant will be summarized in:

- A separate treatment regimen (ie, Crossover) for the safety summaries during the maintenance dosing period (eg. summaries of TEAEs and exposure).
- The initially assigned treatment regimen for all other summaries.

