- Section 9.2.2 was updated to include details of analyses on time to onset of selected TEAEs of special interest. Summaries of longest duration of selected TEAEs of special interest were added to have a better understanding of the safety profile in terms of duration of class-effect AEs as well as AEs influenced by treatment regimens. "Grade 2 or higher" was changed to "Grade 3 or higher" for time to onset summary of rash. This change was made to be consistent with other PI3K inhibitors, which highlighted more severe cutaneous reactions graded as Grade 3 or higher in the labeling. "Herpes simplex virus infection" was changed to "herpes simplex" based on the MedDRA coding dictionary as a broader term. Exfoliative dermatitis was added to the list of TEAEs of special interest.

- Section 9.2.3 was updated to include summary of TEAEs by PT and maximum severity in decreasing order of frequency, summary of longest duration of selected TEAEs of special interest, and additional supporting summaries during the INCB050465 initial QD dosing period and the maintenance dosing period, which will provide supportive data of the safety profile of the maintenance dose. Summary of nonserious TEAEs by SOC and PT was removed because it will not be used for the clinical study report but will be provided for result disclosure.
- Section 9.3.2 was modified to include ALT and AST in the line graphs as additional supportive analyses for laboratory events of special interest.
- Section 9.3.3 was added to identify potential Hy's law events to better monitor liver toxicity.
- Section 9.3.4 was updated to align with the analysis plan for adverse events of special interest. Summary of worsening of laboratory events of special interest was removed because this is covered by the summary of worsening of laboratory abnormalities.
- Section 9.5 was updated to change the high threshold of QTcF and QTcB interval from 460 to 450 milliseconds for purpose of analysis. This change is to comply with the categories outlined in FDA Guidance for Industry (E14 Clinical Evaluation of QT/QTc Interval Prolongation and Proarrhythmic Potential for Non-Antiarrhythmic Drugs) used to characterize outliers in OTc values.

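### The by-period TEAE summaries give raw percentages over an 8-week lead-in and an open-ended maintenance period; first-event rates per time at risk would be a cheap improvement

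*SAP*

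**What the plan says.** SAP 9.2.3 plans overall TEAE summaries by regimen for the "initial QD dosing period, maintenance dosing period, and overall period". Every row is a count and percentage of participants: any, Grade 3 or higher, serious, related and fatal TEAEs, and TEAEs leading to reduction, interruption or discontinuation. Supporting tables by MedDRA term follow for the two dosing periods, including "Summary of TEAEs leading to discontinuation of INCB050465 by SOC and PT". The SAP change log for Amendment 1 gives the purpose of these tables as data "which will provide supportive data of the safety profile of the maintenance dose".

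The periods differ in kind. Protocol Table 4 (5.4.1.1) sets the lead-in at "20 mg QD for 8 weeks (Day 1 through Day 56"). SAP 5.2 states that the weekly dosing period in Group A and "the 2.5 mg QD dosing period in Group B are considered maintenance dosing periods". SAP 3 sets no end date: "Participants may receive treatment until disease progression, death, unacceptable toxicity, or consent withdrawal, whichever occurs first". The Protocol synopsis describes a treatment period for a subject who "has not met withdrawal criteria (approximately 52 weeks").

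Protocol 1.4 gives the reason for stepping down. Of 2.5 mg QD it says that the regimen "could reduce the frequency of AEs that lead to study treatment withdrawal", and it says much the same of weekly dosing.

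Neither SAP 9.2.3 nor the Appendix A table list contains an exposure-adjusted AE rate. SAP 6.4 summarizes treatment duration by period, but in separate exposure tables. SAP 9.2.2 and 9.3.4 plan life-table and Kaplan-Meier time to onset, measured from first dose, for named special-interest and laboratory events.

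**The concern.** A percentage of participants with an event rises with the time they are watched. A fixed 8-week column beside a column that may average about 44 weeks therefore invites a comparison that the numbers cannot bear. The row most exposed is discontinuation due to TEAEs, because Protocol 1.4 gives reducing such events as the reason for both maintenance regimens.

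The same problem runs across the columns within maintenance. Under SAP 5.2, participants who switch after maintenance has started form a separate Crossover group in these tables. Protocol 4.1 allows a switch only for those who have not met withdrawal criteria, so that group stayed on treatment long enough to switch. The 70 later participants all join the selected regimen. Time in maintenance can therefore differ between Group A, Group B and Crossover for reasons unrelated to toxicity.

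The SAP text also does not say whether a maintenance percentage is taken over everyone treated or over those who entered maintenance.

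**Working it through.** The plan states no AE incidence by period, so there is no figure of its own to reproduce. The check is how the planned percentages behave.

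Inputs from the documents:
- Lead-in: 8 weeks (Protocol Table 4).
- Maintenance: about 52 weeks of treatment (Protocol synopsis) minus 8 = 44 weeks.
- A shorter case: median treatment in Study 101 was 114 days (Protocol 1.3). 114/7 = 16.3 weeks, and 16.3 − 8 = 8.3 weeks of maintenance.

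Assumptions: lead-in incidence P, shown over a range; a constant rate within each period; a maintenance rate equal to r times the lead-in rate, with r = 0.5 for a halving.

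Formulas:
- Weekly lead-in rate: λ = −ln(1 − P)/8.
- Maintenance percentage, everyone treated for m weeks: 1 − (1 − P)^(r·m/8).
- Maintenance percentage, exponentially distributed duration with mean m: rλm/(1 + rλm).

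For r = 0.5 and m = 44 the exponent is 0.5 × 44/8 = 2.75:

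| Lead-in (assumed) | Maintenance, fixed 44 weeks | Maintenance, exponential, mean 44 weeks |
|---|---|---|
| 2% | 5.4% | 5.3% |
| 5% | 13.2% | 12.4% |
| 10% | 25.2% | 22.5% |
| 20% | 45.9% | 38.0% |
| 30% | 62.5% | 49.5% |

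With an unchanged rate, 10% in the lead-in becomes 1 − 0.9^5.5 = 44.0% over 44 weeks.

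When the direction changes (fixed duration):
- The two percentages are equal when r·m/8 = 1. For a halved rate this is m = 16 weeks.
- At m = 44, the maintenance rate must fall below 8/44 = 18% of the lead-in rate before its percentage is the lower one.
- At m = 8.3 and r = 0.5, 10% in the lead-in becomes 1 − 0.9^(8.3/16) = 5.3%, so the order reverses.
- Near saturation, with exponential duration and mean 44 weeks, the order reverses once lead-in incidence exceeds about 83% (80% vs 81.6%, but 90% vs 86.4%). The any-TEAE row could be in that region.

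Denominator: if, as an assumption, 15% of treated participants never enter maintenance but stay in the denominator, 25.2% becomes 0.85 × 25.2% = 21.4%.

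The same example as a rate: P = 10% gives λ = 0.0132 per week, or 68.7 per 100 participant-years, and 68.7/12 = 5.7 per 100 participant-months. Half of that is 34.4 per 100 participant-years, or 34.4/12 = 2.9 per 100 participant-months. The ratio of 0.50 is visible, where the percentages would read 10.0% and 25.2%.

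**The case against.** Several points on the other side have force.

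**The 44 weeks is a planning figure.** The only observed duration in the documents, the Study 101 median, would reverse the direction. That median pooled all histologies at a data cut of an ongoing study, so it does not displace this protocol's own figure. It does mean that a reader who infers that maintenance will look more toxic even at half the rate goes further than the documents allow. The result is conditional on duration and on the row.

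**The rate is not constant.** Protocol 5.4.1.4 says most immune-related AEs come after the first 9 weeks. In Study 101 (Protocol 1.3), 12 of 63 subjects stopped treatment for AEs, and all but one of these events came after the 9-week assessment. A reader might infer that exposure-adjusted rates would show whether stepping down reduces toxicity. They would not. No arm continues 20 mg QD, so dose and time on treatment are confounded. With late-onset toxicity the maintenance rate could exceed the lead-in rate even if the lower dose helps. This limits what the rates can mean, but it applies equally to the raw percentages.

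**No comparison between periods is planned.** The SAP excludes statistical comparison between groups and treats the by-term period tables as supporting. No test is invalid. The issue is how a descriptive table reads.

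**Time-at-risk methods already exist in part.** By event type, the life tables in SAP 9.2.2 and 9.3.4 cover 10 of the 12 discontinuation events listed for Study 101; psoriasis and hypercalcemia fall outside, and rash and neutrophil decrease are covered only at the higher grades. These analyses measure onset of an event, not discontinuation because of it, and they give no overall result for serious or Grade 3 or higher TEAEs.

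**The denominator may be settled elsewhere.** Table shells are in a separate document. The text leaves the denominator unstated, and it would be wrong to conclude that it is incorrect.

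**Conclusion.** The point holds as a cheap improvement to descriptive reporting; it does not identify an error or contradiction in the plan. The period percentages in SAP 9.2.3 depend on time at risk, and that time is unequal between periods and can be unequal between Group A, Group B and Crossover.

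At about 44 weeks of maintenance, a halved constant rate would still show as roughly 2.1 to 2.6 times the lead-in percentage for events with 5% to 30% lead-in incidence (62.5/30 and 13.2/5). With exponentially distributed durations it would be about 1.7 to 2.5 times (49.5/30 and 12.4/5). These sizes rest on assumed incidences, a constant rate within each period and the protocol's approximate 52 weeks. Below 16 weeks of maintenance the direction changes for a halved rate.

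The gap matters most for TEAEs leading to discontinuation, interruption or reduction, serious TEAEs, and Grade 3 or higher TEAEs overall, which the planned time-to-onset analyses do not cover.

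**What to change.** In the SAP 9.2.3 period summaries:

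1. State that the denominator for maintenance percentages is participants who entered the maintenance period.
2. Add, by period and regimen column, participants with a first event per 100 participant-months at risk in that period. Do this for any, Grade 3 or higher and serious TEAEs, and for TEAEs leading to discontinuation, interruption or reduction.
3. Define time at risk as running from the start of the period to the first event in it or the end of the period. Say how the 30-day window after the last dose is assigned, how events ongoing from the lead-in are treated, and how time is split at crossover. Also say when maintenance starts for participants moved to weekly dosing before Week 9 for diarrhea or colitis.
4. Add a footnote that between-period contrasts are descriptive and cannot isolate a dose effect, because no arm continues 20 mg QD and the protocol expects most immune-related AEs after week 9.

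The cost is a few rows in tables already planned and a short time-at-risk definition. SAP 6.4 already uses the period dosing dates and AE dates are collected, so no new data are needed. The definition still has to be written, because dosing duration is not the same as time at risk.
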